## 9. STUDY CALENDAR

Activity	Pre-study (to be performed within 45 days of enrollment unless otherwise specified)	RT	Chemo	Primary Outcome Assessment 8 (+/- 4) weeks after Chemo (Time 0)	Follow-up after Time 0 g		
					Every 3 months	Months 3, 6, 12, 18, 24	Months 6, 12, 18, 24
Pregnancy Test a	X						
Biopsy within 180 days of enrollment	X			X e	X e		
Clinical Exam with DRE b	X		X d	X	X		
Procto/Sigmoidoscopy within 90 days of enrollment	X		X d	X	X		
CT chest/abdomen/pelvis c	X		X d	X			X
MRI pelvis	X		X d	X		X	
Labs-CBCD, CMP, CEA	X		X i	X			X
ECOG	X						
HRQOL	X j			X			X f
PET/MRI or FDG-PET c	X			X			
AE evaluation	X j	X	X	X L	X f		
ctDNA	X j	X k		X		X h	

aNegative pregnancy test by urine, for women non-post-menopausal as defined in Appendix.

bDRE may be deferred for clinical reasons, as determined by treating physician.

cMRI abdomen can substitute for CT abdomen/pelvis per physician discretion; PET imaging is *optional*. PET/MRI is preferred.

dRestaging after 8 (+/-4) weeks of chemotherapy. Procto/sigmoidoscopy and CT CAP can be omitted per physician discretion.

eIf biopsy is needed to rule out residual or progressive tumor, per the discretion of the surgeon

fAfter TME, patients will leave surveillance schedule but continue to receive HRQOLs, and be assessed for treatment-related AEs

gFollow-up appointments and activities 2 weeks before and 2 weeks after each timepoint are permitted, and may be completed virtually.

hAmong only those managed with organ preservation

iCEA does not need to be collected; pre-study CBCD, CMP may suffice for cycle 1 Day 1 chemo labs

jActivities to be done after enrollment and before treatment begins

kctDNA will be collected following completion of RT

LAn additional AE evaluation may be scheduled up to 3 months after completion of chemotherapy if needed

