### **12.5.2 Analysis Plan**

For the toxicity outcome, we will calculate the proportion of patients meeting our definition of toxicity. In addition, we will present the frequency and percent of other adverse events reported in the study.

Local regrowth rate will be calculated as the proportion of patients with local regrowth based on the secondary analysis population. The local regrowth rate and its 95% confidence interval will be calculated.

Disease-free survival is defined as the time from start of RT therapy to date of progression or death due to any cause. If a subject is not known to have progressed or died, then DFS will be censored at the latest date the subject was known to be alive or disease-free (on or before the cut-off date). The DFS distribution will be estimated using the Kaplan-Meier method, and the Kaplan-Meier curves, medians and 95% confidence intervals of the medians will be presented.

Colostomy-free survival distribution will be estimated using the Kaplan-Meier method, and the Kaplan-Meier curves, medians and 95% confidence intervals of the medians will be presented.

OS is defined as the time from start of RT therapy to date of death due to any cause. If a subject is not known to have died, then OS will be censored at the latest date the subject was known to be alive (on or before the study end date). The OS distribution will be estimated using the Kaplan-Meier method, and the Kaplan-Meier curves, medians and 95% confidence intervals of the medians will be presented.

For the HRQOL measures, we will calculate the mean and standard deviations of each of the individual indices at baseline and every 3 months during the duration of the study; we will graphically depict scores at each time point. In addition, we will calculate the difference of the QoL scores at the baseline, time of cCR, and last follow up date and report summary statistics.

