## Appendix B: MSKCC Bowel Function Instrument

### MSKCC Bowel Function Instrument

Date: \_\_\_\_ / \_\_\_\_ / \_\_\_\_\_ (mm/dd/yyyy)      Patient Study ID: \_\_\_\_\_

As part of the SHiORT FOX trial, we are very interested in how your function (bowel, bladder, sexual) and quality of life. Below are 19 questions that should take less than 15 minutes to complete so that we can better understand how your life has been affected by rectal cancer therapy

Over the last 4 weeks....

	bowel movements/24 hours				
	Always	Most of the time	Sometimes	Rarely	Never
1. How many bowel movements did you generally have in 24 hours?	bowel movements/24 hours				
2. Do certain solid foods increase the number of bowel movements in a day?					
3. Do certain liquids that you drink increase the number of bowel movements in a day?					
4. Do you feel like you have totally emptied your bowels after a bowel movement?					
5. Do you get to the toilet on time?					
6. Do you have another bowel movement within 15 minutes of your last bowel movement?					
7. Do you know the difference between having to pass gas (air) and needing to have a bowel movement?					
8. Have you used medicines to decrease the number of bowel movements (drugs like Imodium®, Lomotil®)?					
9. Have you had diarrhea (no form, watery stool)?					
10. Have you had loose stool (slight form, but mushy)?					

	Always	Most of the time	Sometimes	Rarely	Never
11. Have you been able to wait 15 minutes to get to the toilet when you feel like you are going to have a bowel movement?					
12. Have you been able to control the passage of gas (air)?					
13. Have you limited the types of solid food you eat to control your bowel movements?					
14. Have you limited the types of liquids you drink to control your bowel movements?					
15. Have you had soilage (leakage of stool) of your undergarments during the day?					
16. Have you used a tissue, napkin, and/or pad in your undergarments during the day when you go to bed?					
17. Have you had soilage (leakage of stool) of your undergarments when you go to bed?					
18. How often have you had to alter your activities because of your bowel function?					
19. Compared to 4 weeks ago, how would you rate your bowel function now?					
	Much better than 4 weeks ago				
	Somewhat better than 4 weeks ago				
	About the same as 4 weeks ago				
	Somewhat worse than 4 weeks ago				
	Much worse than 4 weeks ago				

GOOD FUNCTION is HIGH

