MSKCC Published Bowel Function Instrument	Coding Scheme	Subscale
1. Over the last 4 weeks, how many bowel movements do you generally have in 24 hours?	If < 2 score = 5 If $\geq 2$ and $< 3$ score = 4 If $\geq 3$ and $< 4$ score = 3 If $\geq 4$ and $< 5.5$ score = 2 If $\geq 5.5$ score = 1 Must reverse for scoring < 2 bm = 1 2 bm = 2 3 bm = 3 4 - 5.5 = 4 <math>\geq 5.5 = 5</math>	Frequency
2. Do certain solid foods increase the number of bowel movements in a day?	1=Always 5=Never	Diet
3. Do certain liquids that you drink increase the number of bowel movements in a day?	1=Always 5=Never	Diet
4. Do you feel like you have totally emptied your bowels after a bowel movement?	1=Never 5=Always	Separate
5. Do you get to the toilet on time?	1=Never 5=Always	Frequency
6. Do you have another bowel movement within 15 minutes of your last bowel movement?	1=Always 5=Never	Separate
7. Do you know the difference between having to pass gas (air) and needing to have a bowel movement?	1=Never 5=Always	Separate
8. Have you used medicines to decrease the number of bowel movements (drugs like Imodium®, Lomotil®)?	1=Always 5=Never	Frequency
9. Have you had diarrhea (no form, watery stool)?	1=Always 5=Never	Frequency
10. Have you had loose stool (slight form, but mushy)?	1=Always 5=Never	Frequency
11. Have you been able to wait 15 minutes to get to the toilet when you feel like you are going to have a bowel movement?	1=Never 5=Always	Frequency
12. Have you been able to control the passage of gas (air)?	1=Never 5=Always	Separate
13. Have you limited the types of solid food you eat to control your bowel movements?	1=Always 5=Never	Diet
14. Have you limited the types of liquids you drink to control your bowel movements?	1=Always 5=Never	Diet
15. Have you had soilage (leakage of stool) of your undergarments during the day?	1=Always 5=Never	Urgency/soilage
16. Have you used a tissue, napkin, and/or pad in your undergarments during the day in case of stool leakage?	1=Always 5=Never	Urgency/soilage
17. Have you had soilage (leakage of stool) of your	1=Always 5=Never	Urgency/Soilage

undergarments when you go to bed?		lage
18. How often have you had to alter your activities because of your bowel function?	1=Always 5=Never	Urgency/Soilage
19. Compared to 4 weeks ago, how would you rate your bowel function now?	1=Always 5=Never	Separate

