For question 1, high scores indicate good bowel function.

Questions 4, 5, 7, 11, and 12 are bolded to indicate reverse scoring codes (1=Never, 5=Always).

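### Appendix B and Section 12.5.2 contain HRQOL scoring and timing rules that cannot be followed as written; the repair is wording, and the cCR result is untouched

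*Combined protocol and SAP*

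**What the plan says.** **Question 1.** The Appendix B scoring table gives a plain list for movements per 24 hours: below 2 scores 5, 2 to below 3 scores 4, 3 to below 4 scores 3, 4 to below 5.5 scores 2, and 5.5 or more scores 1. In the same cell, after "Must reverse for scoring", a bold list gives below 2 the code 1, 2 the code 2, 3 the code 3, 4 to 5.5 the code 4, and 5.5 or more the code 5. The form carries the line "GOOD FUNCTION is HIGH", and the note under the table says "For question 1, high scores indicate good bowel function".

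**Item 19.** The item reads "19. Compared to 4 weeks ago, how would you rate your bowel function now". Its five answers start at "Much better than 4 weeks ago" and end at the matching worst category. The scoring table codes it from 1 for Always to 5 for Never and marks it as a Separate item.

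**Timing.** Section 12.5.2 plans means and standard deviations of each index "at baseline and every 3 months during the duration of the study". It adds differences between baseline, time of cCR and last follow-up. In the Section 9 calendar the HRQOL row is marked before treatment, at Time 0, and in the column headed "Months 6, 12, 18, 24". It is blank under RT, under chemotherapy and in the three-monthly column. Section 10.3 says forms are collected at every assessment visit and refers to the calendar. Section 12.5.1 applies the HRQOL analysis to the whole primary analysis population.

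**The concern.** An analyst working from Appendix B alone has to choose between two opposite scores for question 1, and cannot score item 19 with the codes given. The bold type adds to the risk. The note under the table explains bold as marking reversed codes for questions 4, 5, 7, 11 and 12, and for those items the bold codes are the ones to apply. Question 1 is not in that list, but someone carrying the convention over would use the bold list. Fewer bowel movements would then lower the Frequency score. Bowel function is a main functional outcome for an organ-preservation programme.

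The timing rules raise a separate problem. Some of the summaries in 12.5.2 have no scheduled form behind them. One of the differences is tied to an event that non-responders, who are in the analysis population, do not have if the phrase is taken literally.

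**Working it through.** **The plan's own figure.** The only calculated figure used here is the sample size of 37 (Section 12.6.2). Exact enumeration of the two-stage rule (stop at 3 or fewer of 17, reject the null at 11 or more of 37) gives a rejection probability of 0.0948 at a cCR rate of 0.2 and 0.903 at 0.4. This agrees with the stated 0.1 and 0.9. The figure is not in dispute.

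**1. Question 1 under both lists.**

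| Movements per 24 h | Plain list | Bold list | Bold minus plain |
|---|---|---|---|
| 1 | 5 | 1 | -4 |
| 2 | 4 | 2 | -2 |
| 2.5 | 4 | none | – |
| 3 | 3 | 3 | 0 |
| 3.5 | 3 | none | – |
| 4 or 5 | 2 | 4 | +2 |
| 5.5 | 1 | 4 and 5 | +3 or +4 |
| 6 | 1 | 5 | +4 |

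The plain list covers every value once. The bold list leaves gaps at 2.5 and 3.5 and codes 5.5 twice. Only the plain list agrees with the two statements that high is good.

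**2. Size if the bold list were the final score.** Let x be the plain score. The bold score is 6 - x, so the error in one score is (6 - x) - x = 6 - 2x, which is 0, 2 or 4 points in size.
- The Frequency items are 1, 5, 8, 9, 10 and 11. Appendix B gives no combining rule, so a plain sum is assumed: range 6 to 30, width 24.
- Single score: 2/24 = 8.3% and 4/24 = 16.7% of the width.
- A true change of d categories would appear as -d, an error of 2d. That is 2 points (8.3%) for one category. It reaches 8 points (8/24 = 33.3%) only for a patient who moves between the two extreme categories.
- If the bold list holds raw codes to be reversed, then 6 - (6 - x) = x and the error is 0.

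**3. Item 19.** Always and Never are not among its answers, so the stated codes cannot be assigned. Numbering the answers in the order of the form would give 5 to the worst category, against the statement that high is good. The item is in none of the three named subscales (Frequency, Diet, Urgency/soilage).

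**4. Schedule after Time 0.** The three-monthly points to month 24 are 3, 6, 9, 12, 15, 18, 21 and 24, which is 8. Forms are scheduled at 6, 12, 18 and 24, which is 4. Months 3, 9, 15 and 21 have none. The calendar's window is stated as "Follow-up appointments and activities 2 weeks before and 2 weeks after each timepoint are permitted". Two weeks is about 0.5 month, while the nearest form is 3 months away.

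**5. Schedule before Time 0.** Without delays, the time from start of RT is about 1 week of RT, a gap of 2 to 4 weeks, chemotherapy of 16 weeks (8 × 14 days) or 18 weeks (6 × 21 days), then 4 to 12 weeks.
- Shortest: 1 + 2 + 16 + 4 = 23 weeks.
- Longest: 1 + 4 + 18 + 12 = 35 weeks.
- At 4.345 weeks per month this is 5.3 to 8.1 months, with no form scheduled between the baseline form and Time 0.

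On a clock started at baseline, month 3 is therefore always empty and month 6 may be. That is a different clock from step 4, so the two counts must not be added.

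**6. Time of cCR.** Read literally, patients without cCR have no such time: 37 × 0.6 = 22.2 at a rate of 0.4 and 37 × 0.8 = 29.6 at 0.2. Read as Time 0, every assessed patient has a scheduled form.

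**The case against.** Several counter-arguments have force.

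- **The direction of question 1 is settled.** Two statements in Appendix B say that high is good, and the bold list can be read as raw codes. This stands, so a reader should not infer that the bowel scores will be inverted. What remains is that the list is unlabelled and incomplete and follows an instruction to reverse.
- **Item 19 is a stand-alone item.** Nothing shows that it enters a total. This stands, and it limits the effect, but the coding still cannot be applied.
- **Section 10.3 may itself schedule three-monthly forms.** Its reference to the calendar could simply point to the list of visits, which includes a three-monthly column; the HRQOL row would then be the outlier. This is a fair reading, so one cannot say that no three-monthly forms exist. Section 4.2.5, however, sends HRQOL for patients who have TME to the calendar. On either reading the three places disagree.
- **Time of cCR naturally means the Time 0 assessment.** This is accepted. The figures of 22 and 30 patients tempt a reader to infer that most patients would lack HRQOL data at that point. The documents do not support that, because the calendar schedules a form for everyone assessed at Time 0. The ambiguity remains for a near-complete responder observed to a later timepoint under Section 4.2.5.
- **Last follow-up is a legitimate descriptive summary.** True, but it mixes lengths of follow-up. Forms continue after TME and stop once a patient is treated for progression.

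**Conclusion.** The point holds as a minor one. Three faults are plain in the text: two opposite codings of question 1, a coding of item 19 that does not fit its answers, and three-monthly summaries that lack a scheduled form at 4 of the 8 points after Time 0. The wording of time of cCR and last follow-up is a lesser matter of clarity.

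The question 1 error ranges from zero (raw codes) to 4 points on the item. The share of 4 in 24 rests on an assumed plain sum of six items. The schedule count rests on the HRQOL row of the calendar as printed and on a clock that starts at Time 0. Summaries without forms would be empty, not biased.

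A reader might infer that the trial's main result is at risk. It is not. HRQOL is named among the secondary objectives but is an exploratory endpoint in the Synopsis and Section 10.3, its analysis is descriptive, and it plays no part in the cCR analysis, the stopping rules or the Section 12.7 criteria.

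**What to change.** **Appendix B.** Keep one coding of question 1, with high meaning good and cut-points that neither overlap nor leave gaps; the plain list meets this. Delete the bold list or label it as raw codes. Code item 19 to its own five answers, with high meaning good. Check both against the published scoring that Section 10.3 cites before finalising them. Recompute any existing question 1 scores from the recorded number of movements, and check how any item 19 answers were entered.

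**Sections 12.5.2, 10.3 and 9.** Make the three agree: summarise at baseline, Time 0 and months 6, 12, 18 and 24. Also report any three-monthly forms already collected under 10.3, so that they are not lost. Replace time of cCR by Time 0, and use Time 0 also for a patient whose cCR is declared later. Beside last follow-up, report change from baseline at the fixed calendar months with the number of patients who have both forms. Fixed months do not recover forms missing after progression, so state that number as well.

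**Cost.** Wording in these sections, and some rescoring if scoring has begun. No new visits, forms or data.

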## Appendix C: Low Anterior Resection Syndrome (LARS)

Low Anterior Resection Syndrome Score – LARS Score. English version 1.0

### Bowel function questionnaire

**The aim of this questionnaire is to assess your bowel function.**

**Please tick only one box for each question. It may be difficult to select only one answer, as we know that for some patients symptoms vary from day to day. We would kindly ask you to choose one answer which best describes your daily life. If you have recently had an infection affecting your bowel function, please do not take this into account and focus on answering questions to reflect your usual daily bowel function.**

---

**Do you ever have occasions when you cannot control your flatus (wind)?**

- No, never
- Yes, less than once per week
- Yes, at least once per week

**Do you ever have any accidental leakage of liquid stool?**

- No, never
- Yes, less than once per week
- Yes, at least once per week

**How often do you open your bowels?**

- More than 7 times per day (24 hours)
- 4-7 times per day (24 hours)
- 1-3 times per day (24 hours)
- Less than once per day (24 hours)

**Do you ever have to open your bowels again within one hour of the last bowel opening?**

- No, never
- Yes, less than once per week
- Yes, at least once per week

**Do you ever have such a strong urge to open your bowels that you have to rush to the toilet?**

- No, never
- Yes, less than once per week
- Yes, at least once per week

## The LARS Score - Scoring Instructions

Add the scores from each 5 questions to one final score.

### Do you ever have occasions when you cannot control your flatus (wind)?

 No, never	0
 Yes, less than once per week	4
 Yes, at least once per week	7

### Do you ever have any accidental leakage of liquid stool?

 No, never	0
 Yes, less than once per week	3
 Yes, at least once per week	3

### How often do you open your bowels?

 More than 7 times per day (24 hours)	4
 4-7 times per day (24 hours)	2
 1-3 times per day (24 hours)	0
 Less than once per day (24 hours)	5

### Do you ever have to open your bowels again within one hour of the last bowel opening?

 No, never	0
 Yes, less than once per week	9
 Yes, at least once per week	11

### Do you ever have such a strong urge to open your bowels that you have to rush to the toilet?

 No, never	0
 Yes, less than once per week	11
 Yes, at least once per week	16

**Total Score:** \_\_\_\_\_

#### Interpretation:

**0-20:** No LARS  
**21-29:** Minor LARS  
**30-42:** Major LARS

## Appendix D: Stoma QOL

### The Stoma Quality of Life Scale (SQOLS) Questionnaire

We would like to use your opinions and experiences to help us improve the care of individuals with ostomies. Please read each statement and decide the way it applies to you. Some questions may seem to be more important to you than others; however, try to answer all questions to the best of your ability. Your responses are confidential.

#### Part 1

1. Rate your **overall** satisfaction with *your life in general right now* on a scale of 0 to 100, with 0 being totally unsatisfied and 100 being totally satisfied.
2. Rate your **overall** satisfaction with *your life in general during the last month* on a scale of 0 to 100, with 0 being totally unsatisfied and 100 being totally satisfied.

#### Part 2

Never (1) Seldom (2) Occasionally (3) Frequently (4) Always (5)

For each of the following questions, please choose a number from the choices above that corresponds to your answer.

3. I am able to participate in hobbies that I enjoy. \_\_\_\_\_
4. I am able to go out with friends. \_\_\_\_\_
5. My stoma interferes with my ability to work or attend school. \_\_\_\_\_
6. I worry about traveling because of my stoma. \_\_\_\_\_
7. I enjoy sexual activity. \_\_\_\_\_
8. I feel attractive. \_\_\_\_\_
9. My sexual partner is bothered by my stoma. \_\_\_\_\_
10. It bothers me if others are aware I have a stoma. \_\_\_\_\_
11. I worry about lack of privacy when I need to empty my pouch. \_\_\_\_\_
12. I feel comfortable in my clothing. \_\_\_\_\_
13. I am satisfied with the foods I eat. \_\_\_\_\_
14. I have financial concerns regarding my ostomy supplies. \_\_\_\_\_
15. I have problems with odor. \_\_\_\_\_
16. I am able to share my feelings and concerns about my ostomy with a family member or friend. \_\_\_\_\_
17. I am embarrassed by gas (noises or rapid filling of bag). \_\_\_\_\_
18. I worry my ostomy appliance will leak. \_\_\_\_\_
19. I am bothered by skin irritation around the stoma. \_\_\_\_\_
20. Social situations make me feel anxious. \_\_\_\_\_
21. I perform the same household and family duties. \_\_\_\_\_

## Appendix 2 Suggested Scoring of the SQOLS

### Part 1

Overall satisfaction with life is scored from 0 to 100. Question 1 reflects current satisfaction and may be more useful when changes over short periods of time are important. Question 2 reflects satisfaction during the previous month.

### Part 2

- Work/Social Function Scale =  $25 \times (12 + \text{Que3} + \text{Que4} - \text{Que5} - \text{Que6} - \text{Que20} + \text{Que21})/6$
- Sexuality/Body Image =  $25 \times (1 + \text{Que7} + \text{Que8} - \text{Que9} + \text{Que12} + \text{Que16})/5$
- Stoma Function =  $25 \times (24 - \text{Que10} - \text{Que11} + \text{Que13} - \text{Que15} - \text{Que17} - \text{Que18})/6$
- Financial Concerns =  $25 \times (5 - \text{Que14})$
- Skin Irritation =  $25 \times (5 - \text{Que19})$

If any two questions are missing for a subscale, the entire subscale should be set to missing. If one is missing, the scale score can be prorated.

## Appendix E: International Index of Erectile Function (IIEF-5)

### The IIEF-5 Questionnaire (SHIM)

Please encircle the response that best describes you for the following five questions:

Over the past 6 months:					
1. How do you rate your confidence that you could get and keep an erection?	Very low 1	Low 2	Moderate 3	High 4	Very high 5
2. When you had erections with sexual stimulation, how often were your erections hard enough for penetration?	Almost never or never 1	A few times (much less than half the time) 2	Sometimes (about half the time) 3	Most times (much more than half the time) 4	Almost always or always 5
3. During sexual intercourse, how often were you able to maintain your erection after you had penetrated your partner?	Almost never or never 1	A few times (much less than half the time) 2	Sometimes (about half the time) 3	Most times (much more than half the time) 4	Almost always or always 5
4. During sexual intercourse, how difficult was it to maintain your erection to completion of intercourse?	Extremely difficult 1	Very difficult 2	Difficult 3	Slightly difficult 4	Not difficult 5
5. When you attempted sexual intercourse, how often was it satisfactory for you?	Almost never or never 1	A few times (much less than half the time) 2	Sometimes (about half the time) 3	Most times (much more than half the time) 4	Almost always or always 5

**Total Score:** \_\_\_\_\_

1-7: Severe ED    8-11: Moderate ED    12-16: Mild-moderate ED    17-21: Mild ED    22-25: No ED

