### **4.2 Treatment Schedule**

Study treatment will start within 30 days of eligibility determination.

Treatment will comprise 6 daily fractions of RT at 5 Gy per fraction followed 2-4 weeks later by approximately 4 months of chemotherapy.

Patients will be assessed for the primary outcome approximately 8 weeks (+/- 4 weeks) following completion of chemotherapy. Those who are not eligible for organ preservation will proceed with TME. All others will undergo organ preservation and surveillance for local regrowth for 2 years on protocol.

Treatment will be administered on an outpatient basis. No investigational or commercial agents or therapies other than those described may be administered with the intent to treat the patient's malignancy.

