##### **4.2.2.1 FOLFOXIRI**

- Oxaliplatin 85mg/m^2 IV Day 1, dose rate per institutional standard of care
- Leucovorin 400 mg/m^2 IV Day 1 (optional), dose rate per institutional standard of care
- Irinotecan 165mg/m^2 IV Day 1, dose rate per institutional standard of care
- 5-Fluorouracil 3200mg/m^2 IVI Day 1, over 48 hours
- 14-day cycle for 8 cycles
- If necessary to accommodate holidays, patient schedule or other justified circumstances, schedule may be modified by +/- 7 days

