#### **4.2.4 Assessment of primary endpoint**

Patients' responses to therapy will be evaluated clinically 8 (+/-4) weeks after completion of radiation and chemotherapy.

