## Appendix F: 6-item Female Sexual Functionality Index

### FSFI-6 Questionnaire

How would you rate your level (degree) of sexual desire or interest?

Very high	High	Moderate	Low	Very low or none at all
5	4	3	2	1

How would you rate your level of sexual arousal ("turn on") during sexual activity or intercourse?

No sexual activity	Very high	High	Moderate	Low	Very low or none at all
0	5	4	3	2	1

How often did you become lubricated ("wet") during sexual activity or intercourse?

No sexual activity	Almost always or always	Most times	Sometimes	A few times	Almost never or never
0	5	4	3	2	1

When you had sexual stimulation or intercourse, how often did you reach orgasm?

No sexual activity	Almost always or always	Most times	Sometimes	A few times	Almost never or never
0	5	4	3	2	1

How satisfied have you been with your overall sexual life?

Very satisfied	Moderately satisfied	About equally satisfied and dissatisfied	Moderately dissatisfied	Very dissatisfied
5	4	3	2	1

How often did you experience discomfort or pain during vaginal penetration?

Did not attempt intercourse	Almost never or never	A few times	Sometimes	Most times	Almost always or always
0	5	4	3	2	1

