## Appendix G: International Prostate Symptom Score

### International Prostate Symptom Score (I-PSS)

Patient Name: \_\_\_\_\_ Date of birth: \_\_\_\_\_ Date completed: \_\_\_\_\_

In the past month:	Not at All	Less than 1 in 5 Times	Less than Half the Time	About Half the Time	More than Half the Time	Almost Always	Your score
1. Incomplete Emptying How often have you had the sensation of not emptying your bladder?	0	1	2	3	4	5	
2. Frequency How often have you had to urinate less than every two hours?	0	1	2	3	4	5	
3. Intermittency How often have you found you stopped and started again several times when you urinated?	0	1	2	3	4	5	
4. Urgency How often have you found it difficult to postpone urination?	0	1	2	3	4	5	
5. Weak Stream How often have you had a weak urinary stream?	0	1	2	3	4	5	
6. Straining How often have you had to strain to start urination?	0	1	2	3	4	5	
	None	1 Time	2 Times	3 Times	4 Times	5 Times	
7. Nocturia How many times did you typically get up at night to urinate?	0	1	2	3	4	5	
Total I-PSS Score							

**Score:** 1-7: *Mild* 8-19: *Moderate* 20-35: *Severe*

Quality of Life Due to Urinary Symptoms	Delighted	Pleased	Mostly Satisfied	Mixed	Mostly Dissatisfied	Unhappy	Terrible
If you were to spend the rest of your life with your urinary condition just the way it is now, how would you feel about that?	0	1	2	3	4	5	6

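### At Time 0 the men's 6-month sexual-function score describes mostly the chemotherapy period, and the women's form as printed states no recall period (minor)

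*Combined protocol and SAP*

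**What the plan says.** - **Men's form.** Appendix E heads the IIEF-5 items with "Over the past 6 months".
- **Women's form.** Appendix F opens directly with "How would you rate your level (degree) of sexual desire or interest". No reference period is shown for any item, and several items are in the past tense.
- **Timing.** Section 4.2 gives RT "followed 2-4 weeks later by approximately 4 months of chemotherapy". Under section 4.2.4, response is "evaluated clinically 8 (+/-4) weeks after completion of radiation and chemotherapy". The Study Calendar calls that visit Time 0.
- **HRQOL visits.** Section 4.1 and the Study Calendar place HRQOL after enrollment but before treatment, at Time 0, and at months 6, 12, 18 and 24, with two weeks' allowance either side in follow-up.
- **Analysis.** Section 12.5.2 will "calculate the difference of the QoL scores at the baseline, time of cCR, and last follow up date". It also plans means and standard deviations every 3 months, a schedule the Study Calendar does not show for HRQOL. It says nothing about recall periods and treats all indices alike.
- **Other forms.** The bowel form covers 4 weeks, the I-PSS asks about symptoms "In the past month", and the EQ-5D asks about today.

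**The concern.** A difference between visits is easy to interpret only if each score describes the patient at about the time of that visit. At Time 0 the IIEF-5 reaches back through most of chemotherapy, while the bowel, bladder and EQ-5D forms completed on the same day describe the weeks after it. A reader of the planned summaries would naturally take the Time 0 value as early post-treatment function. On that reading, baseline-to-Time 0 partly measures function during chemotherapy. Time 0-to-last-visit could also show improvement merely because later windows no longer contain chemotherapy.

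For women the difficulty is different. With no stated period, two respondents, or one respondent at two visits, may describe different lengths of time, and the analyst cannot recover afterwards which was meant.

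Section 2 lists sexual dysfunction among the harms of TME that organ preservation may avoid, and section 1.2 includes longitudinal functional outcomes among the objectives. The sexual-function trajectory is therefore likely to be reported and read.

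**Working it through.** **Inputs**
- Recall window: 6 months at 30.44 days = 182.6 days (Appendix E).
- Chemotherapy: "14-day cycle for 8 cycles" for FOLFOXIRI, with the same schedule for mFOLFIRINOX and FOLFOX; six 21-day cycles for XELOX (4.2.2.1 to 4.2.2.4).
- Time 0: 28, 56 or 84 days after chemotherapy (4.2.4).
- Gap between RT and chemotherapy: 14 to 28 days (4.2). RT is taken as about one week.
- Assumptions: the time of cCR means Time 0, there are no cycle delays, and the form is completed on the visit date.

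**Step 1. Reproduce the stated length of chemotherapy**
- 8 × 14 = 112 days; 112 / 30.44 = 3.7 months.
- 6 × 21 = 126 days; 126 / 30.44 = 4.1 months.

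Both agree with the stated figure of approximately 4 months.

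**Step 2. Divide the Time 0 window**

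Let d be the days from the end of chemotherapy to Time 0, and C the length of chemotherapy.
- Post-chemotherapy share = d / 182.6
- Chemotherapy share = min(C, 182.6 − d) / 182.6

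| Time 0 after chemotherapy | Post-chemotherapy | Chemotherapy, C = 112 | Chemotherapy, C = 126 |
|---|---|---|---|
| 4 weeks (d = 28) | 28/182.6 = 15% | 112/182.6 = 61% | 126/182.6 = 69% |
| 8 weeks (d = 56) | 56/182.6 = 31% | 112/182.6 = 61% | 126/182.6 = 69% |
| 12 weeks (d = 84) | 84/182.6 = 46% | 98.6/182.6 = 54% | 98.6/182.6 = 54% |

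Any remainder is the RT-to-chemotherapy gap, RT itself or time before treatment. It is largest at 4 weeks with 14-day cycles: 182.6 − 28 − 112 = 42.6 days, or 23%.

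**Step 3. Sensitivity**

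If chemotherapy is taken to end with the last dosing rather than the end of the last cycle, C is about 100 days (14-day cycles) or 119 days (XELOX). The chemotherapy share is then 100/182.6 = 55% or 119/182.6 = 65% at 4 or 8 weeks, and 54% at 12 weeks. In every scenario more than half of the window is chemotherapy time.

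**Step 4. Later visits**

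The month 6 window starts at Time 0 (6 × 30.44 − 182.6 = 0), or 14 days before it if the visit is two weeks early. Chemotherapy ended at least 28 days before Time 0, so the window contains no chemotherapy days. Months 12, 18 and 24 are clear as well.

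If a form were given at month 3, as the 3-monthly summaries in 12.5.2 might suggest, the window would reach 91.3 days before Time 0, or 105.3 days with an early visit. It would then hold up to 105.3 − 28 = 77.3 chemotherapy days. With Time 0 at 12 weeks and a visit two weeks late it would hold none.

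**Step 5. What this means for the planned differences in men**

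| Difference | Status with respect to chemotherapy |
|---|---|
| Baseline to Time 0 | Mixed: the Time 0 window is 54% to 69% chemotherapy |
| Time 0 to last visit | Mixed, for the same reason |
| Baseline to last visit | Clear if the last form is month 6 or later |

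For comparison, a 4-week window at Time 0 contains no chemotherapy days, because Time 0 is at least 28 days out. A one-month window contains at most 30.4 − 28, or about 2 days.

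**The case against.** Much can be said for the plan, and several stronger readings that a reader might infer do not stand.

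- **That none of the planned differences measures post-treatment change.** This is wrong for men. Baseline precedes treatment, and from month 6 the window lies after chemotherapy, so baseline-to-last-visit is already a usable contrast in 12.5.2. The exception is a man whose last form is the Time 0 form, for example because HRQOL stopped when he was treated for progression (4.2.5).
- **That the Time 0 artefact flatters organ preservation.** The documents do not support this. The study has one arm (2.4). HRQOL is summarised in the whole treated population, so TME and organ-preservation patients are pooled (12.5.1), and no comparison between them is planned. The carry-over affects both groups at Time 0. Nor does 12.5.2 call Time 0-to-last-visit recovery; the risk is that a reader will.
- **That change in women is undefined.** A missing window makes the reference period ambiguous. It does not show that scores at dated visits fail to track change, since women may well answer for the recent past. The percentages above apply to men only.
- **That the sexual-function forms alone depart from short, fixed windows.** Section 10.3 accepts that the LARS has no specific period, and Part 2 of the Stoma QOL prints none.

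It is also fair to say that HRQOL is exploratory in the synopsis and section 10.3, although section 1.2 lists it as a secondary objective. It carries no test and plays no part in the success criteria of 12.7. A header line on the FSFI-6 may also have been lost in conversion from PDF.

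What survives is that the male Time 0 value is mostly an on-treatment value, that two planned differences use it without saying so, and that the FSFI-6 as printed needs a recall period.

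**Conclusion.** The point holds in a limited form and is minor. For men, 54% to 69% of the period recalled at Time 0 is chemotherapy time and 15% to 46% follows it, so baseline-to-Time 0 and Time 0-to-last-visit mix on-treatment with post-treatment function. Baseline-to-last-visit remains valid with respect to chemotherapy when the last form is from month 6 or later. For women, the period described is ambiguous if the form in use matches the printed one.

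The conclusion depends on the assumptions listed with the inputs; cycle delays would tend to raise the chemotherapy share. The documents do not allow a check of whether 6 months is the validated IIEF-5 window, so nothing here faults the instrument itself. The direction and size of any effect on scores cannot be derived from the documents. The primary endpoint and the safety rule are not affected.

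**What to change.** **In 12.5.2, for men:**
- Label the Time 0 sexual-function value as largely on-treatment.
- Report change from baseline to fixed visits, months 12 and 24, with the number of men contributing. Month 6 is less suitable because its window runs from Time 0 and can straddle TME. A later operation, for example after regrowth, can still fall in a later window and should be noted.
- Do not interpret Time 0-to-last-visit as recovery.

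The IIEF-5 wording stays as printed.

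**For the FSFI-6:** first check whether the form in use carries a recall line. If it does not, print one, for example the past 4 weeks as on the bowel form. That length is only a suggestion, since the documents state no intended period. Flag the forms collected without the line, or analyse them separately.

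**Cost:** a few sentences in 12.5.2 and one header line, with no new visit or change in sample size. The drawbacks are that men have no clean post-treatment value at Time 0, men without a month 12 or 24 form do not contribute to those contrasts, and earlier FSFI-6 forms are only partly comparable with later ones.
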